mg), as this will, in effect, enable us to compare selective ER beta agonism with mixed (ER alpha and beta) agonism, since the higher 75 mg dose could mitigate the recurrence of depressive symptoms by acting through ER alpha. We also will monitor other possible targets of ER alpha activation in these postmenopausal women including plasma luteinizing hormone (LH) levels, plasma prolactin secretion, and endometrial thickness (by vaginal ultrasound). These measures were selected for the following reasons: First, plasma LH levels are increased in postmenopausal women, and studies in mice demonstrate that ER alpha is responsible for ongoing negative feedback effects of estradiol on pituitary LH secretion ³²⁻³⁴; consequently, LY500307-related decreases in plasma LH levels would suggest an ER alpha action. Second, prolactin secretion also has been identified in preclinical studies to be mediated by ER alpha ^{35,36}; consequently, an LY500307-related increase in plasma prolactin secretion would suggest ER alpha activity. Finally, increased endometrial tissue, as measured by vaginal ultrasound, also would suggest the presence of ER alpha activity. These additional outcomes will assist in our efforts to distinguish ER beta activity from ER alpha activity in this protocol.

Medication Administered in this Protocol

Selective Estrogen Receptor beta agonist LY500307: LY500307 is an orally active, selective estrogen receptor beta (ER beta) agonist designed to maximize binding to the ER beta receptor and minimize binding to the estrogen receptor alpha (ER alpha). LY500307 was initially developed for the treatment of benign prostate hyperplasia (BPH). However, due to inadequate efficacy in prostate volume reduction or improvement in International Prostate Symptom Score (IPSS), the benefit-to-risk balance failed to support further development of LY500307 for the BPH indication. LY500307 was selected for use in this protocol since it is the only ER beta selective agonist that both has been

approved by the FDA for use under an IND (held by Lilly) in humans and has evidence to support its ability to penetrate the central nervous system.

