All participants will be instructed to ingest study medications on an empty stomach after an overnight fast, since in all clinical pharmacology studies, LY500307 was administered orally after overnight fast, followed by breakfast approximately 30 minutes after the dosing. The effect of food on LY500307 has not been formally assessed. All participants will receive three capsules of LY500307 or placebo each morning consisting of the following formulations: 1) women randomized to 75 mg LY500307 will receive three capsules each containing 25 mg LY500307; 2) women randomized to 25 mg LY500307 will receive one capsule containing 25 mg LY500307 and two capsules of placebo; and 3) women randomized to placebo will receive three capsules each containing placebo. There will be a 1-1-1 distribution of women in each study arm (i.e., each arm will contain 15 women). A table of random numbers will be used for randomization in this trial. A set of numbers, equivalent to the proposed “N” will be selected and an appropriate block size within that set will be chosen. Within that block, the highest third of the numbers will be assigned to one treatment arm, the middle third will be assigned to the second treatment arm, and the lowest third will be assigned to a third treatment arm. The block size is not revealed to the investigator.

Genetics Studies: Subjects will be invited to provide a 30ml blood sample for genetic characterization studies, including investigation of specific gene polymorphisms (e.g., estrogen, progesterone and androgen receptors) and establishment of lymphoblastoid cell lines (LCLs) and induced pluripotent cell (IPCs) for epigenomic (WES), and transcriptomic (WTS) sequencing. We also plan to perform whole genomic sequencing (WGS) in this protocol in the future. The potential relevance of genetic polymorphisms for women with menstrual cycle-related mood disorders is evidenced in our recent studies (Dubey et. al, 2017; Rudzinskas et. al, 2020), where we have

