After the three-week baseline period and the determination that ET does not precipitate symptoms, women will be randomized to one of three arms as follows: LY500307 at a dose of 25 mg per day, LY500307 at a dose of 75 mg per day, or matched placebo for three weeks. Once the three weeks of LY500307 or placebo treatment is completed, non-menstruating women will receive one week of Provera (5 mg/day) at the end of the trial to induce a progestin withdrawal bleed. The justification for employing two separate doses of LY500307 is that the lower dose (i.e., 25 mg) may be insufficient to effectively produce agonist effects at ER beta. Prevention of the emergence of estradiol withdrawal-induced mood symptoms at the 75 mg dose (but not the 25 mg dose) would suggest either a dose-dependent agonism at ER beta or the requirement for activation of ER alpha. The latter possibility will be examined by monitoring ER α activity at the levels of the endometrium, the pituitary (plasma LH and prolactin), and possibly hypothalamus (plasma LH³³), which will help us evaluate potential ER alpha actions accompanying the higher dose of LY500307. Of note, the 75 mg daily dose is within the safety margins established by Lilly.

After the trial, those women who were taking ET prior to the study will be re-started on their previous HT regimen unless they request to continue the withdrawal from HT under medical supervision. Outcome measures will include standardized mood and behavioral rating scales. The main comparisons in this study will be between LY500307 and placebo in women with a past history of perimenopause-related depression. Results will be analyzed by analysis of variance for mixed effects and post-hoc Bonferroni testing.

Weekly visits and daily mood ratings:

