ET (three weekly measures) and DB treatment (three weekly measures). Analyses will be performed with SAS Version 9.2 software (SAS Institute, Inc, Cary, NC), using PROC MIXED (for mixed models). For each symptom rating and blood hormone level, the predictor variables of interest, DB treatment (placebo or LY500307), will be modeled as fixed effects. The covariance pattern across time will be structured as first-order autoregressive. We will use the Kenward-Roger method for computing the degrees of freedom for tests of fixed effects.

For each of the symptom outcomes, we will perform analyses to explore the effect of DB medication in the two treatment groups. We will first examine if symptoms changed from baseline (i.e., OL ET [weeks 1-3 of the trial]) to DB treatment phase (i.e., weeks 4-6 of the trial) in any of the three randomization groups (as described above). For the second analysis, if necessary, we will include the mean of the baseline (OL ET) symptom measure (for each symptom) as a covariate and compare differences in symptom ratings across each of the three randomization groups to test for effects of DB treatment. Plasma levels of estradiol, estrone, prolactin, LH and FSH during DB treatment also will be analyzed across randomization groups. For all analyses the value of the estimator (“least square means” in SAS terminology) and associated standard error of the estimator and p values will be reported. The p values will be adjusted for multiple comparisons ($k=3-6$) by the Bonferroni method, and two-sided $P < 0.05$ will be considered statistically significant.

Clinical characteristics (tables 1-3) in women with past PMD will be compared to ensure similarity across groups and include the following measures: age, BMI, menstrual bleeding, weekly average hot-flush severity scores > 2 (minimal severity), CES-D scores > 16 (consistent with clinically significant depressive symptoms of at least moderate severity ^{1;96}), and CES-D scores > 8 and < 16 (consistent with subsyndromal depression ⁹⁷⁻⁹⁹). We will employ Fisher’s exact test for categorical variables and Student’s t-tests for continuous variables.

b. Power analysis

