Based on the results of protocol 03-M-0175 ¹² and with standardized differences of .6 to .7 (and consistent with a prior meta-analysis of estrogen's effects on depressed mood ¹⁰⁰), 10 -15 women will be required in each of the three treatment cells to achieve a power of 80% with an $\alpha = 0.05$ to detect a significant difference between LY500307 and placebo with analyses of variance with repeated measures and Bonferroni t-tests in the principal outcome measures of HRSD and CES-D scales ¹⁰¹. We intend to recruit up to 80 women for this trial through this protocol. Dropouts will be replaced. Since LY500307 has never been administered to women, there is no data available to estimate the sample size needed to evaluate safety measures. Safety measures (unblinded) including symptom inventories, clinical evaluations, laboratory results, and results of EKG of all women participating in this study will be reviewed by the DSMB.

11. Human Subjects Protection

Subject selection:

a. Subject selection will be equitable. All subjects must meet the inclusion and exclusion criteria listed in Section 4. We will select physically healthy adult female individuals. The proportion of ethnic minorities (vs. Caucasians) in the total sample will be approximately consistent with the overall U.S. population proportions. The specified age range for participants in this study (i.e., ages 45 – 65 years) was selected to match the sample selection criteria we previously employed in protocol 03-M-0175. The lower age limit was to avoid enrolling women with early menopause prior to age 45 and the upper age limit would restrict participants to those who had menopause by age 55 (and therefore not women who had menopause after age 55 years). Thus we wish to study women who experienced menopause within the more normal range between ages 45 and 55 years.

b. Justification for exclusion of children:

We will exclude children or minors because the study population is women with past

perimenopausal depression.

c. Justification for exclusion of vulnerable subjects:

Those without consent capacity are excluded because the research question can be answered by enrolling only adults who can provide their own consent and there is no direct benefit for these participants. Therefore, the risks outweigh the benefits for this population.

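### The plan reads success at 75 mg but not at 25 mg as a dose effect without requiring evidence that the two doses differ

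*Combined protocol and SAP*

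**What the plan says.** Section 1 and the Section 4d rationale give the reasons for a second dose. Section 1 says two doses will "enable us to compare selective ER beta agonism with mixed (ER alpha and beta) agonism". Section 4d (Double-blinded Randomization phase) adds that the lower dose may be too weak at ER beta, and that "Prevention of the emergence of estradiol withdrawal-induced mood symptoms at the 75 mg dose (but not the 25 mg dose) would suggest either" dose-dependent agonism at ER beta or a need to activate ER alpha. It then says the ER alpha possibility will be examined through the endometrium, LH and prolactin.

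The same section states: "The main comparisons in this study will be between LY500307 and placebo". Section 9a repeats this and names CES-D and HRSD as the primary measures. Section 10a first tests each arm against its own open-label baseline. It then, with a conditional phrase, compares ratings across the three groups in a mixed model, with Bonferroni adjustment for k = 3 to 6. The members of that family are not listed. *Prevention* is not defined anywhere, and no section makes the dose reading depend on a comparison of the two doses.

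**The concern.** Both explanations offered in Section 4d assume that the mood effect truly differs between 75 mg and 25 mg. Chance is not among them. A significant comparison with placebo at one dose and a non-significant one at the other is a difference in verdicts, not evidence of a difference in effects, and with 15 per arm such verdicts can easily diverge.

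At stake is the mechanistic conclusion that the second dose was added to support. If the doses are equally effective and the verdicts happen to split this way, the text as written leads to dose dependence or ER alpha. The risk is compounded because Section 1 expects ER beta selectivity to fall with dose. The 75 mg arm could therefore move the ER alpha markers while mood effects are equal, and a chance split would then look like confirmation.

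**Working it through.** **Inputs.** Section 4a: "There will be a 1-1-1 distribution of women in each study arm (i.e., each arm will contain 15 women". Section 10b: "with standardized differences of .6 to .7" and "10 -15 women will be required in each of the three treatment cells to achieve a power of 80" per cent. Section 10a: "two-sided $P < 0.05$ will be considered statistically significant". Assumed for the check: both doses have the same true effect, equal variances, and no dropout.

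**The plan's own figure.** For one measure per woman, n = 2(1.960 + 0.842)²/d². This gives 43.6 (44 per arm) at d = 0.6 and 32.04 (33 per arm) at d = 0.7, not 10-15. Repeated measures can close the gap. For the change between two three-week means with constant correlation 0.5, the variance factor is 2[(1 + 2×0.5)/3 − 0.5] = 0.333, which gives 15 and 11. The within-woman correlation is not stated, so the figure can be neither confirmed nor refuted. The check was therefore run both at the claimed power and at 0.6-0.7 on the analysed scale.

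**Chance of the pattern.** The two comparisons share the placebo arm, so with equal n their test statistics correlate at 0.5. Write δ = d√(n/2) and z for the critical value. Then

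P(75 mg significant, 25 mg not) = Φ(δ − z) − Φ₂(δ − z, δ − z; 0.5).

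- At 80% power: 0.800 − 0.687 = 0.113. With n = 15 and z = 1.960 this is d = 2.802 × √(2/15) = 1.023.
- At d = 0.6: δ = 1.643, and 0.376 − 0.218 = 0.158.
- At d = 0.7: δ = 1.917, and the result is about 0.166.
- The maximum, at 50% power, is 0.500 − 0.333 = 0.167.

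**Simulation** with pooled-variance t-tests (15 per arm, 42 df, 400,000 runs, equal true effects):

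| d | Threshold | Power v placebo | 75 mg but not 25 mg | Same, and direct contrast significant |
|---|---|---|---|---|
| 0.6 | 0.05 | 36% | 15.2% | 1.9% |
| 0.7 | 0.05 | 47% | 16.1% | 2.0% |
| 1.023 | 0.05 | 78% | 11.7% | 1.5% |
| 0.6 | 0.0167 | 21% | 11.3% | 0.6% |
| 0.7 | 0.0167 | 29% | 13.7% | 0.7% |
| 1.023 | 0.0167 | 62% | 15.2% | 0.7% |

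**Within-arm reading.** If *prevention* is judged from each arm's own change from baseline, the arms are independent and the one-direction probability is p(1 − p), where p is the chance that an arm meets the criterion. This is 0.8 × 0.2 = 16% at p = 0.8, and at most 25%. The flaw is the same.

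**Power of the direct contrast.** If 25 mg has half the effect of 75 mg, unadjusted power is about 13% (75 mg effect 0.6), 16% (0.7) and 29% (1.023).

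**The case against.** The sentence is a hedged rationale for using two doses, not a decision rule. It sets no significance criterion and does not itself mention placebo. That is fair, but both explanations it offers still presuppose a true dose difference.

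The remedy may also be partly in the plan. Section 10a compares the three groups, and three arms have three pairwise comparisons, so k = 3 is consistent with 75 mg versus 25 mg being among them. A reader might infer that the plan leaves out the dose comparison altogether; the documents do not support that. What stands is that the contrast is not named, the across-group step is conditional, and the Section 4d reading does not depend on it.

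A reader might also infer that the plan would attribute a split result straight to ER alpha. It would not: LH, prolactin and the endometrium are to be examined first. Those markers help separate the two explanations, but they do not show that mood effects differ by dose.

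It is tempting to say that, when 75 mg succeeds, 25 mg fails by chance in 38% of trials (0.05) or 50% (0.0167). Those figures take d = 0.65 on the analysed scale, where power is only about 41% and 25%, against the 80% claimed in Section 10b. At 80% power and 0.05 the conditional share is about 14% (0.113/0.800).

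Finally, the primary objective concerns LY500307 against placebo, which this point leaves untouched.

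**Conclusion.** The concern holds as a faulty inference about dose, not as a fault in the comparisons with placebo. With equally effective doses, the pattern in the named direction occurs on one primary scale in roughly 1 trial in 9 at the claimed power and 1 in 6 if 0.6-0.7 applies to the analysed scale, both at unadjusted 0.05. With Bonferroni k = 3 the range is about 11-15%.

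These figures rest on 15 analysed women per arm, equal variances and a single scale. The plan does not say whether the pattern must appear on both CES-D and HRSD. If it must, and the scales correlate at 0.5-0.7 (an assumption), the chance falls to about 3-7%; if either scale suffices, it rises above the single-scale figure. The conclusion does not require the sample size in Section 10b to be wrong.

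**What to change.** State in Sections 4d and 10a that any claim of dose dependence, or of a need for ER alpha, rests on the direct 75 mg minus 25 mg difference in double-blind CES-D and HRSD from the planned mixed model, reported with its confidence interval. Name this contrast in the Bonferroni family. If the interval includes zero, report discordant results against placebo as inconclusive about a dose difference: neither evidence of a difference nor evidence of equivalence. Keep the ER alpha markers for interpreting a dose difference once one has been shown.

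In the simulated cases, also requiring the direct contrast cuts the false dose reading to about 1.5-2% at 0.05 and about 0.6-0.7% at 0.0167. The cost is a sentence in each section and one contrast from a model already planned, with no added women or visits. The downside is the contrast's low power, about 13-29% for a half-size effect at 25 mg. A dose difference will seldom be claimed, and the estimate and interval will have to carry the message.

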During the seven-week study, the effects of LY500307 or placebo on mood symptoms will be monitored with daily symptom rating scales and weekly clinic visits. Outcome measures include the following: Primary outcome measures: self ratings - the Center for Epidemiologic Studies-Depression Scale (CES-D)⁴⁷, observer ratings - the 17-item Hamilton Rating Scale of Depression (HRSD)⁴⁸. Secondary outcome measures: the daily symptom rating form (DRF)⁴⁹ consisting of a 14 item six point likert-type scale measuring the severity of several mood and behavior symptoms including hot flushes (completed on a daily basis at home by each participant); the Beck Depression Inventory (BDI)⁵⁰; a visual analogue scale (VAS) measuring the reported severity of 13 mood and behavioral symptoms (completed at each weekly clinic visit); and whole genome expression/exome sequencing.

During eight weekly clinic visits all women will also have blood pressure, pulse, and weight measured and will be assessed for any side effects to the prescribed medications (including specific evaluations of any complaints of calf pain or other symptoms and signs of blood clots in the legs). In addition, blood samples will be drawn via venipuncture at each of the first seven clinic visits; approximately 50 ml of blood will be collected at each draw (total = 350 ml). This blood will be analyzed for several measures such as the following: estradiol, estrone, FSH, LH, prolactin, testosterone, dihydrotestosterone, SHBG, electrolytes; glucose, CBC, renal, hepatic, thyroid and lipid functions. These measures will be employed to monitor safety parameters of LY500307 (i.e., CBC, renal, hepatic, thyroid and lipid functions), and the potential effects of LY500307 on measures of ER alpha function (see above). Blood samples for estradiol will be processed within 24 hours in the NIH Clinical Center Pathology Service and sent to a staff member not involved with patient

care in order to monitor compliance with estradiol therapy.

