After the completion of this trial, all participants will be evaluated for the presence of clinically significant mood symptoms. Additionally, the results (including symptom ratings and plasma hormone levels) of the study will be reviewed with each participant. If negative mood symptoms or distressing hot flushes are present, we will discuss therapeutic options prior to referral of each participant back to her community health care provider. Additionally, all women will be requested to return for a follow-up clinic visit four weeks after completion of the seven week medication phase (i.e., three week open estradiol treatment, three week double blind placebo/ LY500307 treatment, and one week progestin treatment in non-menstruating women) to evaluate possible adverse effects emerging post-treatment – although no late-onset adverse effects are anticipated. At the time of this follow-up visit an EKG will be performed on all subjects to assess QTc. The options for follow-up in those women who report persisting negative mood symptoms include no treatment with follow-up by community health care provider, initiation of standard antidepressant therapy such as selective serotonin uptake inhibitors with follow-up in community, or resumption of previous menopausal hormone therapy by her community health care provider. Our experience in protocol 03-M-0175, which employed a similar study design with a symptom-provocation paradigm, suggests that in the majority of women depressive symptoms that emerged during estradiol withdrawal were of mild to moderate severity and time-limited. In those women in whom depressive symptoms persisted and were accompanied by distress, either resuming their previous ET or commencing standard antidepressant therapy led to a remission of symptoms. However, in

the fourteen women with past perimenopausal depression who participated in 03-M-0175 and were randomized to estradiol withdrawal, only three women elected to resume ET or use antidepressant therapy because of distressing mood symptoms.

5. Management of Data and Samples

a. Storage

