Subjects are evaluated by one of the Associate Investigators or the PI. Overall participant safety will be monitored by the PI. During weekly clinic visits all women will have blood pressure, pulse, and weight measured and will be assessed for any side effects to the prescribed medications (including specific evaluations of any complaints of calf pain or other symptoms and signs of blood clots in the legs). After completing the study (including the one month follow-up evaluation in every woman), participants will either be discharged from this protocol with a referral to the community, or will be referred to other NIMH studies.

Patients will be instructed not to become pregnant during the study and sexually active women will be required to employ barrier contraceptive methods.

The Investigators will consult with the Independent Medical Monitor, the NIMH Office of the Clinical Director and the Human Subjects Protection Unit (HSPU) team throughout study participation around issues of participant safety. Participants will be assessed for adverse experiences by the investigator. The reasons for study withdrawal include:

- a. Clinically significant abnormal lab values or adverse events inconsistent with continuation in the protocol.
- b. Clinical judgment of the investigator, the multidisciplinary team, or Independent Medical Monitor. The multidisciplinary team will meet throughout the week to coordinate treatment efforts, monitor the progress/safety of the patient and determine whether further participation would put the patient's safety at risk. The multidisciplinary team will make regular (i.e., every 3 weeks) on the clinical status of the participant to the Independent Medical Monitor. If the participant demonstrates clinical worsening (whether through clinical observation or scores on the CGI), the Independent Medical Monitor may recommend that the participant be withdrawn from protocol.

Other members of the multidisciplinary team also reserve the right to discontinue a participant from

further participation for any reason.

- c. Withdrawal of consent and/or patient decision to terminate.

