activities for multiple studies and obtaining consent for each one is beyond their resources. The subjects will be provided with additional pertinent information after participation as they will be informed whether or not they are eligible to sign a consent for additional screening.

14. Data and Safety Monitoring

a. Data and safety monitor:

The protocol will be monitored by the NIMH-IRP Data and Safety Monitoring Board (DSMB). The NIMH-IRP DSMB SOP and membership is on file with the IRB.

b. Data and safety monitoring plan:

This study will be reviewed by the NIMH DSMB prior to implementation and at least twice annually. Additional reviews may be scheduled at the discretion of the DSMB. The DSMB will review study accrual and progress, adverse events related to the study and safety and outcome data as well as other study specific data elements at their request. The medically responsible investigator has the authority to break the blind in the event of an emergency. Breaking of the blind, life threatening injury or death all require immediate reporting to the DSMB and the NIMH Clinical Director. A written notification to the DSMB chair must follow within 7 days. Results of the DSMB review are provided to the PI, the Clinical Director and the IRB.

The PI is responsible for participants in this protocol and will report all serious adverse events to the NIMH Clinical Director and the IRB within the guidelines set by the standards for clinical research within the NIH intramural research program.

As part of the Clinical Operations Committee, the Principal Investigator (PI) and Associate Investigators will discuss subjects' participation during weekly rounds and will review all data and procedures. During weekly clinic visits all women will also have blood pressure, pulse, and weight measured and will be assessed for any side effects to the prescribed medications (including specific

evaluations of any complaints of calf pain or other symptoms and signs of blood clots in the legs).

The PI will be ultimately responsible for monitoring the data and safety and will provide continuous, close monitoring of adverse events. A yearly summary of adverse event data will be reported to the NIH IRB and the external Data and Safety Monitoring Board (DSMB).

c. Criteria for stopping the study or suspending enrollment or procedures:

In the event of unanticipated problems or serious side effects, the PI will consider whether the study should continue.

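### The plan does not keep LH, FSH, prolactin and SHBG results from whoever rates HRSD, which leaves room to guess the arm in weeks 4 to 6, chiefly for 75 mg versus placebo

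*Combined protocol and SAP*

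**What the plan says.** - **What is measured.** Section 4.d (Weekly visits and daily mood ratings) takes blood at the first seven weekly visits. The analytes include "estradiol, estrone, FSH, LH, prolactin, testosterone, dihydrotestosterone, SHBG", together with routine safety chemistry. The stated uses are safety monitoring and assessment of ER alpha function.
- **What is routed away from care staff.** In the same subsection, estradiol samples alone are "sent to a staff member not involved with patient" "care in order to monitor compliance with estradiol therapy". The reason given is compliance. Blinding is not mentioned.
- **How the other hormones are to be read.** The Introduction says that "LY500307-related decreases in plasma LH levels would suggest an ER alpha action" and that an "LY500307-related increase in plasma prolactin secretion would suggest ER alpha activity". Section 4.d ties LH, prolactin and the endometrium to possible ER alpha action at the higher dose. Section 9.b adds FSH and lipids as markers, and Section 2.b adds SHBG.
- **Who sees data and who evaluates.** Section 14.b has the PI and Associate Investigators discuss each woman's "participation during weekly rounds and will review all data" and procedures. Section 8 states: "Subjects are evaluated by one of the Associate Investigators or the PI".
- **The outcome.** Sections 4.d and 9.a name HRSD as an observer-rated primary outcome, alongside the self-rated CES-D. Section 10.a analyses three weekly ratings in the double-blind phase (weeks 4 to 6) and holds the randomization code until all 45 women have finished.

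**The concern.** HRSD depends on an observer's judgement, so it is protected only while the observer cannot guess the arm. Capsules are matched, but a weekly hormone panel is a second possible source of information. Each woman also has her own values on open-label estradiol from weeks 1 to 3. If LH is suppressed through ER alpha, as the Introduction argues, it should rise after withdrawal on placebo and might stay lower on 75 mg. Someone who follows the weekly values could see that contrast while still scoring HRSD.

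Estradiol is a weak clue, because all three arms stop the patch. The one restricted route therefore covers one of the less informative results, while those that the protocol itself treats as signs of drug action have no restriction. At stake are the validity of one of the two primary outcomes and, less directly, withdrawal decisions that Section 8 leaves partly to clinical judgement.

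**Working it through.** The plan gives no figure on this point, so the main check is to set the relevant text side by side.

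**1. Is any result other than estradiol withheld?** No. Section 4.d restricts estradiol only. Sections 5.a and 19.a give data access to the study investigators as one group, without separating raters from others.

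**2. Is the HRSD rater identified or shielded?** No. No section names an independent rater or says that raters lack access to laboratory results. Section 8 has the PI or an Associate Investigator evaluate the women, and Section 14.b has the same roles review all data, with no exception for hormones.

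**3. Which ratings are open to influence?** Assume that blood is drawn and HRSD is rated at the same visit, and that results return within a week (the documents give a 24-hour processing time for estradiol only). A visit's own result then cannot affect that visit's rating. The first double-blind rating is protected, and the second and third of the three are open.

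**4. What about ultrasound?** The first scan precedes randomization and cannot hint at the arm. The second follows three weeks of double-blind treatment. It can touch at most the last rating, and only if it is read beforehand.

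**5. Which comparison is exposed?** The Introduction describes 25 mg as the dose with the best ER beta selectivity and expects ER alpha effects to grow with dose. The exposure is therefore mainly 75 mg versus placebo. CES-D is self-rated and is not reached by this route in weeks 4 to 6.

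**6. Illustration of consequence.** Inputs from the plan: 15 women per arm, two-sided 5%, and Bonferroni adjustment with k = 3 to 6. Assumption not in the documents: a spurious shift of b SD in the analysed score of one arm, with no true effect.

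For a two-sample t-test, df = 15 + 15 − 2 = 28. The non-centrality is b / √(2/15) = b / 0.365, which is 0.548 for b = 0.2 and 0.822 for b = 0.3. The rejection probability is the two-tailed area of the non-central t distribution beyond the critical value.

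| Assumed shift (SD) | Error at nominal 5% | Error at 0.05/3 = 1.67% |
|---|---|---|
| 0 | 5.0% | 1.7% |
| 0.1 | 5.8% | 2.0% |
| 0.2 | 8.3% | 3.2% |
| 0.3 | 12.5% | 5.4% |

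This is a simple t-test, not the planned repeated-measures model. It shows only what a modest rater shift could do at this sample size. The point does not depend on it.

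**The case against.** The strongest reply is that the plan nowhere says the HRSD rater sees these results. The sentence on weekly rounds is general safety-monitoring text, and the sentence on who evaluates the women also sits in a safety section without mentioning HRSD. Other text refers to a psychiatrist, psychiatric nurse or social worker as screening interviewers. No release time is given for LH, FSH, prolactin or SHBG. All of this stands. It means that access is permitted, not shown. It does not remove the gap, because nothing in the plan prevents access.

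A reader might infer several stronger things that the documents do not support:

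- **That hormone results are known to reach raters.** This would need a statement on who rates HRSD and when results are released. There is none.
- **That raters learn an arm-to-hormone pattern from women who have finished.** Section 4.e does say that "the results (including symptom ratings and plasma hormone levels) of the study will be reviewed with each participant". But this follows completion, so it cannot affect that woman's own double-blind ratings, and arms stay masked until all 45 women are done. Hormone values without arm labels confirm no pattern.
- **That any bias favours the study hypothesis.** The markers track ER alpha. Section 4.d says that benefit at 75 mg alone could reflect ER alpha activation, which would not cleanly confirm an ER beta effect. The direction of bias is unknown.
- **That the estradiol routing is a blinding barrier left incomplete.** Its stated purpose is compliance.

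It is also fair that the clue is hypothetical. The drug has not been given to women before, so no hormone signature is established and a rater would be guessing from the protocol's own expectations.

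**Conclusion.** The concern holds in limited form. As written, the plan allows whoever rates HRSD to see LH, FSH, prolactin and SHBG during weeks 4 to 6. The protocol lists these among its markers of ER alpha action. The exposure falls mainly on 75 mg versus placebo, most likely on the later double-blind ratings, and on HRSD rather than CES-D. Ultrasound adds little.

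This conclusion rests on the general wording of Sections 8 and 14.b and on the absence of any rule shielding the rater. Whether raters would look, what they would infer, and how far and in which direction scores would move cannot be determined from the documents. The rise from 5% to 8.3 to 12.5% follows only from the assumed shift of 0.2 to 0.3 SD. The change is worth making because it lowers the risk of bias in a primary outcome at little cost; the point does not show that the trial would be unblinded.

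**What to change.** - In Section 4.d, extend the existing estradiol routing to LH, FSH, prolactin, SHBG, estrone and the androgens, and add protection of the blind as a stated purpose.
- In Section 14.b, exclude these results from weekly rounds until the blind is broken.
- State who rates HRSD. Add that the rater does not see these hormone results, nor the endometrial thickness from the second ultrasound before the woman's last double-blind rating.
- Keep safety laboratory tests and any clinically abnormal finding visible to the responsible clinician. Lipids serve both as a safety test and as an ER alpha marker, so they stay visible for safety. Where roles allow, the clinician who reads them should not be the HRSD rater.

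The cost is protocol wording and the extension of a routing that already exists, with no new procedure or staff. The downside is that investigators see non-safety hormone results later.
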